6.15.2 Handheld Dynamometry (HHD)

HHD will be measured at Day 0 pre-dose, Day 30, Day 60 pre-dose, Day 84, Day 120 pre-dose, Day 144 and Day 180.

Maximal values of strength of each muscle group of 3 trials and their changes from baseline will be presented with descriptive statistics for each visit by treatment group (Table 14.6.2, Listing 16.2.9.2).

6.15.3 Accurate test of limb isometric strength (ATLIS)

ATLIS will be measured (only at sites that have the ATLIS equipment) at Day 0 pre-dose, Day 30, Day 60 pre-dose, Day 84, Day 120 pre-dose, Day 144 and Day 180.

Values of muscle strength of each muscle group and their changes from baseline will be presented with descriptive statistics for each visit by treatment group (Table 14.6.3, Listing 16.2.9.3).

6.15.4 Amyotrophic Lateral Sclerosis Assessment Questionnaire, 40 questions (ALSAQ-40)

ALSAQ-40 will be measured at Day 0 pre-dose, Day 84 and Day 180.

Values of each question and their changes from baseline will be presented with descriptive statistics for each visit by treatment group (Table 14.6.4.1 and 14.6.4.2, Listing 16.2.9.4).

The subscales (physical mobility, activities of daily living/independence, eating and drinking, communication, and emotional functioning) will be presented with descriptive statistics for values on each visit and changes from baseline for each post-baseline visit (Tables 14.6.4.3 and 14.6.4.4).

6.15.5 Clinical Global Impression of Change (CGIC) and Patient Global Impression of Change (PGIC)

QMD Ref: Worldwide-TMP-ST-005-7.0 Effective: 12Aug2019	Governing QMD: Worldwide-SOP-ST-001
Confidentiality Statement	

This document is the property of Worldwide Clinical Trials Inc. and may not be duplicated, copied, altered or removed from company without prior approval from Worldwide Quality Assurance or in compliance with Worldwide Standard Operating Procedures.

Worldwide Clinical Trials Controlled Quality Management Document			
 WORLDWIDE CLINICAL TRIALS	Sponsor:	Helixmith Co., Ltd.	
Protocol Number:			VMALS-002-2
STATISTICAL ANALYSIS PLAN VERSION 3.0			

CGIC and PGIC will be measured at Day 84 and Day 180.

CGIC (Global improvement and Efficacy index) and PGIC (Impression of change and Degree of Change) will be presented with descriptive statistics for each visit by treatment group (Tables 14.6.5 and 14.6.6, Listings 16.2.9.5 and 16.2.9.6).

6.15.6 Slow vital capacity (SVC)

SVC will be measured at Screening, Day 0 pre-dose, Day 30, Day 60 pre-dose, Day 84, Day 120 pre-dose, Day 144 and Day 180.

Best vital capacity, second best vital capacity and third best vital capacity will be presented with descriptive statistics by visits and treatment group (Table 14.6.7). Also this data and other data collected (% predicted, number of trials and using face mask) will be listed (Listing 16.2.9.7).

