### 5.1. Inclusion Criteria

1. Male or female Participants age  $\geq$  18 years, but  $\leq$  80 years, at time of completion of the informed consent process
2. Clinically definite or probable Amyotrophic Lateral Sclerosis (ALS) or laboratory-supported probable ALS as defined in the revised El Escorial/Airlie House diagnostic criteria
3. The site of onset of ALS symptoms is a limb and experiencing symptoms of lower motor dysfunction (e.g., weakness, atrophy, cramps, poor circulation, etc.) with upper motor neuron symptoms (e.g., brisk reflexes, spasticity)
4. Onset of ALS symptoms  $\leq$  4 years
5. Slow Vital Capacity (SVC)  $\geq$  50% of predicted value at Screening
6. Not taking riluzole, or on a stable dose (defined as no noted toxicities) for at least 30 days prior to Screening and throughout the study
7. Not taking edaravone or on a maintenance cycle for at least 30 days prior to Screening and throughout the study
8. For females of childbearing potential, a negative urine pregnancy test at Screening and on Day 0
9. Male Participants and their female partners must agree to use double-barrier contraception during the study or provide proof of postmenopausal state (minimum 1 year) or surgical sterility
10. Male Participants must not donate sperm during the study
11. Female Participants must be nonpregnant, nonlactating, and either postmenopausal for at least 1 year, or surgically sterile for at least 3 months, or agree to use double-barrier contraception from 28 days prior to randomization (Day 0) and/or their last confirmed menstrual period prior to study randomization (whichever is longer) until the end of the study
12. Capable of complying and willing to comply with the requirements and restrictions in the informed consent form and this protocol
13. Willing to forgo new experimental ALS treatments for at least 6 months following randomization

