### **5.3. Number of Participants**

The target sample size is 18 Participants who will be randomized in a 2:1 ratio to Engensis or Placebo (12:6).

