3.2 Exploratory Endpoints

- Change from Baseline (Day 0) in total mean Revised Amyotrophic Lateral Sclerosis Function Rating (ALSFRS-R) scores at Day 180 for Engensis compared to Placebo
- Change from Baseline (Day 0) in ALSFRS-R subscores for Fine and Gross Motor Functions (sum of scores for items 4 to 9) and for Bulbar Function (sum of scores for items 1 to 3) on Days 30, 60, 84, 120, 144, and 180 for Engensis compared to Placebo
- Changes in the slope of the total ALSFRS-R score over time for Engensis compared to Placebo
- Change from Baseline (Day 0) in muscle strength assessed bilaterally by Handheld Dynamometry (HHD) in muscles in the upper and lower extremities on Days 30, 60, 84, 120, 144, and 180 for Engensis compared to Placebo
- Change from Baseline (Day 0) in the Accurate Test of Limb Isometric Strength (ATLIS) where available at Days 30, 60, 84, 120, 144, and 180 for Engensis compared to Placebo
- Change from Baseline (Day 0) in Quality of Life (QoL) using the ALS Assessment Questionnaire (ALSAQ; with 40 items, ALSAQ-40) on Days 84 and 180 for Engensis compared to Placebo
- Patient Global Impression of Change (PGIC) and Clinical Global Impression of Change (CGIC) at Days 84 and 180 for Engensis compared to Placebo
- Change from Baseline (Day 0) in Slow Vital Capacity (SVC) on Days 30, 60, 84, 120, 144, and 180 for Engensis compared to Placebo
- Time to tracheostomy for Engensis compared to Placebo
- Time to all-cause mortality by Day 180 for Engensis compared to Placebo

QMD Ref: Worldwide-TMP-ST-005-7.0 Effective: 12Aug2019	Governing QMD: Worldwide-SOP-ST-001
Confidentiality Statement	

This document is the property of Worldwide Clinical Trials Inc. and may not be duplicated, copied, altered or removed from company without prior approval from Worldwide Quality Assurance or in compliance with Worldwide Standard Operating Procedures.

Worldwide Clinical Trials Controlled Quality Management Document		
 WORLDWIDE CLINICAL TRIALS	Sponsor:	Helixmith Co., Ltd.
	Protocol Number:	VMALS-002-2
STATISTICAL ANALYSIS PLAN VERSION 3.0		

- Change from Baseline (Day 0) in biomarkers for muscle atrophy in biopsies collected before and after injections for Engensis compared to Placebo

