4 SAMPLE SIZE

A sample size of 18 Participants was chosen for safety assessments and preliminary evaluation of exploratory endpoints.

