5 RANDOMIZATION

Participants are to be randomized on Day 0 as close as possible to the time of the first Study Injections. Randomization will be conducted via an electronic data capture system (EDC) randomization module in a 2:1 ratio for Participants to receive either Engensis or Placebo.

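### SVC is tabulated only as best, second-best and third-best volume, with percent predicted merely listed, so chance imbalance in sex and body size adds avoidable noise at 12 versus 6

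*SAP*

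**What the plan says.** The exploratory endpoint in SAP 3.2 is "Change from Baseline (Day 0) in Slow Vital Capacity (SVC) on Days 30, 60, 84, 120, 144, and 180 for Engensis compared to Placebo". It names no scale, and neither does the matching endpoint in the protocol.

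SAP 6.15.6 sets out the analysis: "Best vital capacity, second best vital capacity and third best vital capacity will be presented with descriptive statistics by visits and treatment group" (Table 14.6.7). It then says that "other data collected (% predicted, number of trials and using face mask) will be listed". In the SAP's list of outputs, Table 14.6.7 is the only SVC table and there is no SVC figure, so no planned output summarises percent predicted by arm.

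The one place where the protocol fixes an SVC scale is inclusion criterion 5 (section 5.1), which sets the entry limit at "50% of predicted value at Screening".

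The target is 18 participants, 12 on Engensis and 6 on Placebo (Protocol 5.3). Randomisation is described only as "in a 2:1 ratio for Participants to receive either Engensis or Placebo" (SAP 5), with no stratification factor. SAP 6.15.6 plans no adjustment for sex, height or age.

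**The concern.** Vital capacity in litres depends on a person's sex, height and age as well as on the state of the respiratory muscles. Percent predicted is meant to take that part out. A table of volumes mixes the two, and with 6 participants in one arm the mix can differ noticeably by chance.

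At stake is how well the trial's only summarised SVC comparison can be read. Part of any difference between arms in Table 14.6.7 will reflect who happened to be allocated where. The table also uses a different scale from the entry criterion, so it cannot show directly how each arm stands relative to the 50% limit.

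**Working it through.** **Inputs from the documents.** 18 participants at 2:1, so 18 × 2/3 = 12 and 18 × 1/3 = 6. There is no SVC mean, SD, effect size or power figure, so the plan has no calculation of its own to reproduce.

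**Assumptions (not in the documents).** Mean predicted volume 4 L with between-person SD 0.5, 0.7 or 0.9 L; baseline 80% predicted (SD 15, kept within 50 to 120); mean loss by Day 180 of 6, 12 or 18 points (SD 10); male share 0.5 to 0.7; percent predicted independent of body size; no treatment effect.

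**Step 1: precision of an arm difference.** SE = SD × √(1/12 + 1/6) = 0.5 × SD. For predicted volume this is 0.25, 0.35 or 0.45 L, with 95% ranges of ±0.49, ±0.69 and ±0.88 L.

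**Step 2: chance of sex imbalance.** With the number of men in each arm binomial (12 and 6), exact enumeration gives a 37% to 41% chance that the arms differ by at least 25 percentage points in share of men, and a 20% to 25% chance of at least 33 points, in either direction.

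**Step 3: shift from body size alone at the 95% limits.**
- Day 180 volume: (80 − loss)/100 × 1.96 × SE. Lowest: 0.62 × 0.49 = 0.30 L. Highest: 0.74 × 0.88 = 0.65 L.
- Change in litres: loss/100 × 1.96 × SE. Lowest: 0.06 × 0.49 = 0.03 L. Highest: 0.18 × 0.88 = 0.16 L.

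For scale, a 12-point loss on 4 L predicted is 0.48 L.

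**Step 4: share of the chance variance of the arm difference explained by imbalance in predicted volume** (squared correlation, 100,000 simulated trials per row):

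| SD of predicted volume (L) | Mean loss (points) | By-visit volume | Change in litres |
|---|---|---|---|
| 0.5 | 6 | 21% | 0.6% |
| 0.5 | 12 | 19% | 2% |
| 0.5 | 18 | 16% | 5% |
| 0.7 | 6 | 34% | 1% |
| 0.7 | 12 | 30% | 4% |
| 0.7 | 18 | 26% | 9% |
| 0.9 | 6 | 46% | 2% |
| 0.9 | 12 | 41% | 7% |
| 0.9 | 18 | 37% | 13% |

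On percent predicted, value or change, the share is 0%. That follows from the independence assumption and is not a finding.

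**Step 5: a worked imbalance.** Assume predicted volume averages 4.5 L in men and 3.1 L in women, with 8 of 12 men on Engensis and 2 of 6 on Placebo. Mean predicted volume is (8 × 4.5 + 4 × 3.1)/12 = 4.03 L against (2 × 4.5 + 4 × 3.1)/6 = 3.57 L. If everyone is at 80% predicted, the arms differ by 0.8 × 0.467 = 0.37 L in level. If everyone then loses exactly 15 points, the losses are 0.605 and 0.535 L, a difference of 0.07 L.

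**Step 6: cost in precision for change.** Take the Step 5 volumes with 60% men, a within-sex CV of 12% and a loss of 15 ± 8 points. The squared CV of predicted volume is about 0.045 and of the loss (8/15)² = 0.284. The relative variance in litres against percent predicted is [(1.045)(1.284) − 1]/0.284 = 1.20. With a mean loss of 10 points the squared CV is 0.64, and the ratio is [(1.045)(1.64) − 1]/0.64 ≈ 1.12. At 1.20 the SE is about 10% larger, since √1.20 = 1.10. The SE of the arm difference in litres is about 0.17 L, so the 0.07 L of Step 5 is about 0.4 SE.

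The same formula at the extremes of the Step 4 grid gives 1.02 (SD 0.5 L, loss 6) and 1.21 (SD 0.9 L, loss 18).

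**The case against.** The strongest reply is that nothing in the documents is contradicted and little hangs on this table. The endpoint names no scale, and an eligibility threshold in percent predicted does not bind an exploratory analysis. SVC is one of eleven exploratory endpoints in a safety study, summarised descriptively without a test, and SAP 4 says only that "A sample size of 18 Participants was chosen for safety assessments and preliminary evaluation of exploratory endpoints". All of that stands, and it limits how much weight the point can carry.

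Second, the larger figures apply to by-visit volumes. Most of the body-size effect would disappear if 6.15.6 named change from baseline, as the endpoint does and as the ALSFRS-R, HHD, ATLIS and ALSAQ-40 sections do. This also stands; for change, what remains is small. SAP 6.2.15 even defines percentage change, which removes body-size scaling, but 6.15.6 does not invoke it.

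Third, an imbalance would be visible, because age, gender, weight, height and BMI are tabulated by arm (SAP 6.6). That is true, but it leaves the reader to guess how far SVC is affected.

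Three stronger readings are tempting but unsupported:
- A reader might infer that the SVC comparison is biased. Allocation is random, so this is chance imbalance. The 0.07 L example is well inside ordinary variation.
- A reader might infer that SVC results cannot be set against the 50% entry limit. Percent predicted is in Listing 16.2.9.7; it is reported but not summarised.
- A reader might infer that tabulating the second- and third-best trials distorts the result. The best value is shown, and the extra rows are a matter of presentation.

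**Conclusion.** The point holds as one of precision and comparability. The only planned SVC summary leaves in variation from sex, height and age that a variable already collected would largely remove. Under the stated assumptions, imbalance in predicted volume accounts for roughly 16% to 46% of the chance variance of the arm difference in by-visit volume, and about 1% to 13% for change in litres. For change, the variance penalty against percent predicted is about 1.1 to 1.2 under the Step 6 inputs, and close to 1 where body size varies little and the mean loss is small.

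The sizes depend on assumed volumes, losses and independence of percent predicted from body size, and on the inference that the tabulated quantities are volumes. The direction depends only on that inference and on volume varying with body size. Because the table is exploratory and descriptive, this is a worthwhile improvement and not a threat to the trial's conclusions.

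**What to change.** In SAP 6.15.6 and Table 14.6.7, add percent predicted SVC from the best trial, with value and change from baseline by visit and arm, and name it as the main SVC summary. Keep best volume as a supporting row and state its units. Moving the second- and third-best trials to Listing 16.2.9.7 is optional.

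The cost is a sentence of SAP text and one revised table shell; percent predicted is already collected. The drawback is that percent predicted depends on the reference equation used.

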6.15.7 Time to tracheostomy

Time to tracheostomy will be presented with descriptive statistics and corresponding survival curves using Kaplan- Meier analysis (Table 14.6.8, Listing 16.2.9.8). The questionnaire is planned to be filled at Screening, Day 0 pre-dose, Day 30, Day 60 pre-dose, Day 84, Day 120 pre-dose, Day 144 and Day 180.

6.15.8 Time to all-cause mortality

Time to all-cause mortality will be presented with descriptive statistics and corresponding survival curves using Kaplan-Meier analysis (Table 14.6.9, Listing 16.2.9.8).

6.15.9 Muscle Atrophy

Information about collected muscle biopsy will be presented in a listing (Listing 16.2.9.9).

7 INTERIM ANALYSIS

No interim analyses are planned.

8 DATA SAFETY MONITORING BOARD ANALYSIS

Data safety monitoring board (DSMB) analyses are described in DSMB Statistical Analysis Plan.

9 CHANGES TO PLANNED PROTOCOL ANALYSIS

There are no changes to the planned protocol analysis.

QMD Ref: Worldwide-TMP-ST-005-7.0 Effective: 12Aug2019	Governing QMD: Worldwide-SOP-ST-001
Confidentiality Statement	
This document is the property of Worldwide Clinical Trials Inc. and may not be duplicated, copied, altered or removed from company without prior approval from Worldwide Quality Assurance or in compliance with Worldwide Standard Operating Procedures.	

Worldwide Clinical Trials Controlled Quality Management Document			
 WORLDWIDE CLINICAL TRIALS	Sponsor:	Helixmith Co., Ltd.	
	Protocol Number:	VMALS-002-2	
STATISTICAL ANALYSIS PLAN VERSION 3.0			

11 LIST OF TABLES, FIGURES AND LISTINGS

Table Number	Table Title	Validation Method	Shell Number (if repeat)
14.1	Demographics Data		
14.1.1	Disposition		
14.1.1.1	Subject Disposition – All Participants Population		
14.1.1.2	Participant Visits – Safety Analysis Population		
14.1.2	Demographics		
14.1.2.1	Demographic and Baseline Characteristics – Safety Analysis Population		
14.1.3	Baseline Characteristics		
14.1.3.1	ALS History – Safety Analysis Population	IP	
14.1.3.2	Prior Medical History - Safety Analysis Population	IP	
14.1.3.3	Ongoing Medical History - Safety Analysis Population	IP	14.1.3.2
14.1.3.4	Familial Cancer History – Safety Analysis Population	IP	
14.2	Efficacy Data		
14.3	Safety Data		
14.3.1	Displays of Adverse Events		
14.3.1.1	Summary of Adverse Events – Safety Analysis Population	IP	
14.3.1.2	Treatment Emergent Adverse Events by System Organ Class and Preferred Term – Safety Analysis Population	IP	
14.3.1.3	Treatment Emergent Serious Adverse Events by System Organ Class and Preferred Term – Safety Analysis Population	IP	
14.3.1.4	Treatment Emergent Adverse Events by System Organ Class and Preferred Term and Maximum Severity – Safety Analysis Population	IP	
14.3.1.5	Treatment Emergent Adverse Events by System Organ Class and Preferred Term and Maximum Relationship – Safety Analysis Population	IP	
14.3.1.6	Treatment Emergent Serious Adverse Events by System Organ Class and Preferred Term and Maximum Severity – Safety Analysis Population	IP	
14.3.1.7	Treatment Emergent Serious Adverse Events by System Organ Class and Preferred Term and Maximum Relationship – Safety Analysis Population	IP	

QMD Ref: Worldwide-TMP-ST-005-7.0 Effective: 12Aug2019	Governing QMD: Worldwide-SOP-ST-001
Confidentiality Statement	

This document is the property of Worldwide Clinical Trials Inc. and may not be duplicated, copied, altered or removed from company without prior approval from Worldwide Quality Assurance or in compliance with Worldwide Standard Operating Procedures.

Worldwide Clinical Trials Controlled Quality Management Document			
 WORLDWIDE CLINICAL TRIALS	Sponsor:	Helixmith Co., Ltd.	
	Protocol Number:	VMALS-002-2	
STATISTICAL ANALYSIS PLAN VERSION 3.0			

Table Number	Table Title	Validation Method	Shell Number (if repeat)
14.3.1.8	Incidence of Injection Site Reactions – Safety Analysis Population	IP	
14.3.1.9	Incidence of Clinically Significant Laboratory Values – Safety Analysis Population	IP	14.3.1.3
14.3.1.10	Adverse Events of Special Interest by System Organ Class and Preferred Term – Safety Analysis Population	IP	
14.3.1.11	Treatment-Emergent Adverse Events leading to study discontinuation by System Organ Class and Preferred Term – Safety Analysis Population	IP	
14.3.1.12	Treatment-Emergent Serious Adverse Events leading to study discontinuation by System Organ Class and Preferred Term – Safety Analysis Population	IP	14.3.1.2
14.3.1.13	Treatment-Emergent Serious Adverse Events leading to study drug withdrawal by System Organ Class and Preferred Term – Safety Analysis Population	IP	14.3.1.3
14.3.1.14	Treatment-Emergent Serious Adverse Events leading to study drug withdrawal by System Organ Class and Preferred Term – Safety Analysis Population	IP	
14.3.1.15	Treatment-Emergent Adverse Events related to study medication by System Organ Class and Preferred Term – Safety Analysis Population	IP	14.3.1.10
14.3.1.16	Treatment-Emergent Serious Adverse Events related to study medication by System Organ Class and Preferred Term – Safety Analysis Population	IP	
14.3.3	Narratives of Deaths, Other Serious and Certain Other Significant Adverse Events		
14.3.4	Abnormal Laboratory Values		
14.3.4.1	Serum Chemistry – Safety Analysis Population	IP	
14.3.4.2	Serum Chemistry, Shift Table – Safety Analysis Population	IP	
14.3.4.3	Hematology – Safety Analysis Population	IP	14.3.4.1
14.3.4.4	Hematology, Shift Table – Safety Analysis Population	IP	14.3.4.2
14.3.5	Exposure to Study Drug		
14.3.5.1	Performed injections – Safety Analysis Population	IP	
14.3.5.2	Amount of Performed Injections – Safety Analysis Population	IP	

QMD Ref: Worldwide-TMP-ST-005-7.0 Effective: 12Aug2019

Governing QMD: Worldwide-SOP-ST-001

Confidentiality Statement

This document is the property of Worldwide Clinical Trials Inc. and may not be duplicated, copied, altered or removed from company without prior approval from Worldwide Quality Assurance or in compliance with Worldwide Standard Operating Procedures.

Worldwide Clinical Trials Controlled Quality Management Document			
 WORLDWIDE CLINICAL TRIALS	Sponsor:	Helixmith Co., Ltd.	
	Protocol Number:	VMALS-002-2	
STATISTICAL ANALYSIS PLAN VERSION 3.0			

Table Number	Table Title	Validation Method	Shell Number (if repeat)
14.3.5.2	Administered volume of Engensis – Safety Analysis Population	IP	
14.3.5.3	Treatment Compliance – Safety Analysis Population	IP	
14.3.6	Vital Signs and Physical Examination		
14.3.6.1	Vital Signs – Safety Analysis Population	IP	
14.3.6.2	Vital Signs, Patients with Clinically Significant Values – Safety Analysis Population	IP	
14.3.6.3	Physical Examination, Shift Table – Safety Analysis Population	IP	
14.3.7	Other Safety		
14.3.7.1	Electrocardiogram – Safety Analysis Population	IP	
14.3.7.2	Electrocardiogram, Shift Table – Safety Analysis Population	IP	
14.3.8	Concomitant Medication		
14.3.8.1	Prior Medications – Safety Analysis Population	IP	
14.3.8.2	Concomitant Medications – Safety Analysis Population	IP	14.3.8.1
14.4	PK Tables		
14.5	PD Tables		
14.6	Other Data		
14.6.1	Revised Amyotrophic Lateral Sclerosis Functional Rating Scale – ITT Population	IP	
14.6.2	Handheld Dynamometry – ITT Population	IP	
14.6.3	Accurate Test of Limb Isometric Strength – ITT Population	IP	14.6.2
14.6.4.1	Amyotrophic Lateral Sclerosis Assessment Questionnaire, 40 questions (worst values imputation) – ITT Population	IP	
14.6.4.2	Amyotrophic Lateral Sclerosis Assessment Questionnaire, 40 questions (average values imputation) – ITT Population	IP	14.6.4.1
14.6.4.3	Amyotrophic Lateral Sclerosis Assessment Questionnaire, subscales (worst values imputation) – ITT Population	IP	
14.6.4.4	Amyotrophic Lateral Sclerosis Assessment Questionnaire, subscales (average values imputation) – ITT Population		14.6.4.3

QMD Ref: Worldwide-TMP-ST-005-7.0 Effective: 12Aug2019

Governing QMD: Worldwide-SOP-ST-001

Confidentiality Statement

This document is the property of Worldwide Clinical Trials Inc. and may not be duplicated, copied, altered or removed from company without prior approval from Worldwide Quality Assurance or in compliance with Worldwide Standard Operating Procedures.

Worldwide Clinical Trials Controlled Quality Management Document			
 WORLDWIDE CLINICAL TRIALS	Sponsor:	Helixmith Co., Ltd.	
	Protocol Number:	VMALS-002-2	
STATISTICAL ANALYSIS PLAN VERSION 3.0			

Table Number	Table Title	Validation Method	Shell Number (if repeat)
14.6.5	Clinical Global Impression of Change – ITT Population	IP	
14.6.6	Patient Global Impression of Change – ITT Population	IP	
14.6.7	Slow Vital Capacity – ITT Population	IP	
14.6.8	Time to Tracheostomy – ITT Population	IP	
14.6.9	Time to All-Cause Mortality – ITT Population	IP	14.6.9

QMD Ref: Worldwide-TMP-ST-005-7.0 Effective: 12Aug2019	Governing QMD: Worldwide-SOP-ST-001
Confidentiality Statement	

This document is the property of Worldwide Clinical Trials Inc. and may not be duplicated, copied, altered or removed from company without prior approval from Worldwide Quality Assurance or in compliance with Worldwide Standard Operating Procedures.

Worldwide Clinical Trials Controlled Quality Management Document			
 WORLDWIDE CLINICAL TRIALS	Sponsor:	Helixmith Co., Ltd.	
	Protocol Number:	VMALS-002-2	
STATISTICAL ANALYSIS PLAN VERSION 3.0			

Figure Number	Figure Title	Validation Method	Shell Number (if repeat)
14.4.1	Exploratory Endpoints		
14.4.1.1	Time to Tracheostomy – ITT Population	IP	
14.4.1.2	Time to All-Cause Death – ITT Population	IP	
14.4.1.3	Revised Amyotrophic Lateral Sclerosis Functional Rating Scale, Total Scores – ITT Population	IP	
14.4.1.4	Revised Amyotrophic Lateral Sclerosis Functional Rating Scale, Subscores for Fine and Gross Motor Function – ITT Population	IP	
14.4.1.5	Revised Amyotrophic Lateral Sclerosis Functional Rating Scale, Subscores for Bulbar Function – ITT Population	IP	

QMD Ref: Worldwide-TMP-ST-005-7.0 Effective: 12Aug2019	Governing QMD: Worldwide-SOP-ST-001
Confidentiality Statement	

This document is the property of Worldwide Clinical Trials Inc. and may not be duplicated, copied, altered or removed from company without prior approval from Worldwide Quality Assurance or in compliance with Worldwide Standard Operating Procedures.

Worldwide Clinical Trials Controlled Quality Management Document			
 WORLDWIDE CLINICAL TRIALS	Sponsor:	Helixmith Co., Ltd.	
	Protocol Number:	VMALS-002-2	
STATISTICAL ANALYSIS PLAN VERSION 3.0			

Listing Number	Listing Title	Validation Method	Shell Number (if repeat)
16.2	Subject Data Listings		
16.2.1	Participant Disposition		
16.2.1.1	Participant Disposition – All Participants Population	IP	
16.2.1.2	Protocol Deviations – Safety Analysis Population	IP	
16.2.4	Demographic		
16.2.4.1	Demographic – Safety Analysis Population	IP	
16.2.4.2	Coagulation Profile – Safety Analysis Population	IP	
16.2.4.3	Viral Screening Results – Safety Analysis Population	IP	
16.2.4.4	Body Measurement – Safety Analysis Population	IP	
16.2.4.5	Amyotrophic Lateral Sclerosis History – Safety Analysis Population	IP	
16.2.4.6	Medical History – Safety Analysis Population	IP	
16.2.4.7	Familial Cancer History – Safety Analysis Population	IP	
16.2.4.8	Prior Medications – Safety Analysis Population	IP	
16.2.4.9	Concomitant Medications – Safety Analysis Population	IP	
16.2.7	Adverse Events		
16.2.7.1	All Adverse Events – Safety Analysis Population	IP	
16.2.7.2	Adverse Events of Special Interest – Safety Analysis Population	IP	
16.2.7.3	Treatment-Emergent Serious Adverse Events – Safety Analysis Population	IP	
16.2.7.4	Injection Site Reactions – Safety Analysis Population	IP	
16.2.7.5	Treatment-Emergent Adverse Events leading to study discontinuation – Safety Analysis Population	IP	
16.2.7.6	Treatment-Emergent Adverse Events related to study medication – Safety Analysis Population	IP	
16.2.7.7	Treatment-Emergent Serious Adverse Events leading to death – Safety Analysis Population	IP	
16.2.8	Individual Laboratory Measurements		
16.2.8.1	Serum Chemistry – Safety Analysis Population	IP	
16.2.8.2	Hematology – Safety Analysis Population	IP	
16.2.8.3	Urine Pregnancy Test Results – Safety Analysis Population	IP	
16.2.8.4	Vital Signs – Safety Analysis Population	IP	
16.2.8.5	Electrocardiogram Results – Safety Analysis Population	IP	

QMD Ref: Worldwide-TMP-ST-005-7.0 Effective: 12Aug2019	Governing QMD: Worldwide-SOP-ST-001
Confidentiality Statement	

This document is the property of Worldwide Clinical Trials Inc. and may not be duplicated, copied, altered or removed from company without prior approval from Worldwide Quality Assurance or in compliance with Worldwide Standard Operating Procedures.

Worldwide Clinical Trials Controlled Quality Management Document			
 WORLDWIDE CLINICAL TRIALS	Sponsor:	Helixmith Co., Ltd.	
	Protocol Number:	VMALS-002-2	
STATISTICAL ANALYSIS PLAN VERSION 3.0			

Listing Number	Listing Title	Validation Method	Shell Number (if repeat)
16.2.8.6	Physical Examination Results – Safety Analysis Population	IP	
16.2.9	Exploratory Data		
16.2.9.1	Revised Amyotrophic Lateral Sclerosis Functional Rating Scale – ITT Population	IP	
16.2.9.2	Handheld Dynamometry – ITT Population	IP	
16.2.9.3	Accurate Test of Limb Isometric Strength – ITT Population	IP	
16.2.9.4	Amyotrophic Lateral Sclerosis Assessment Questionnaire, 40 questions – ITT Population	IP	
16.2.9.5	Clinical Global Impression of Change – ITT Population	IP	
16.2.9.6	Patient Global Impression of Change – ITT Population	IP	
16.2.9.7	Slow Vital Capacity – ITT Population	IP	
16.2.9.8	Time to Tracheostomy and Time to All-Cause Death – ITT Population	IP	
16.2.9.9	Muscle Atrophy – ITT Population	IP	
16.2.10	Exposure to Study Drug		
16.2.10.1	Exposure to Study Drug – Safety Analysis Population	IP	
16.2.10.2	Performed Injections – Safety Analysis Population	IP	
16.2.10.2	Missed Injections – Safety Analysis Population	IP	
16.2.10.3	Compliance – Safety Analysis Population	IP	

QMD Ref: Worldwide-TMP-ST-005-7.0 Effective: 12Aug2019	Governing QMD: Worldwide-SOP-ST-001
Confidentiality Statement	

This document is the property of Worldwide Clinical Trials Inc. and may not be duplicated, copied, altered or removed from company without prior approval from Worldwide Quality Assurance or in compliance with Worldwide Standard Operating Procedures.
